- Placebo treatment group: Patients will receive placebo matching dupilumab Q2W (including doubling the amount of placebo on day 1 to match the loading dose). In order to maintain blinding for the study, patients in the <60 kg weight stratum will receive, in a 1:1 ratio, either placebo matching 200 mg dupilumab (including doubling the amount of placebo on day 1 to match the loading dose) or placebo matching 300 mg dupilumab (including doubling the amount of placebo on day 1 to match the loading dose). In the ≥60 kg weight stratum, the patients randomized to the placebo group will receive placebo matching 300 mg dupilumab (including doubling the amount of placebo on day 1 to match the loading dose).

In order to maintain blinding, all patients will receive an injection Q2W from day 1 to week 14. Patients will receive placebo injection at the weeks dupilumab is not given.

During the treatment period, patients will have weekly in-clinic visits through week 4, and then in-clinic visits every 4 weeks through week 16 with weekly telephone visits in between the in-clinic visits. Patients and/or parents/caregivers (as deemed appropriate based on age of patient) will be trained on injecting study drug during in-clinic visit 2 (day 1) to visit 6 (week 4). During weeks in which no in-clinic visit is scheduled, patients will either self-inject study drug or the parent/caregiver will administer study drug to the patient. In case patients do not want to self-inject and the parent/caregiver do not want to administer study drug to patient, patients may have the clinic staff administer all the study drug injections in the clinic. Safety, laboratory, and clinical assessments will be performed at specified clinic visits, as noted in schedule of event [Appendix 10.2](#). The end of treatment period visit will occur at week 16, two weeks after the last dose of study drug. The co-primary endpoints will be assessed at this visit. If patients prematurely discontinue study treatment, the patients will be encouraged to stay in the study to have data collected at all remaining scheduled visits until completion of the planned end of study visit.

Patients who participate in the study may subsequently be eligible to participate in an open-label extension study.

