#### 4.4.2. Secondary Efficacy Variables

The key secondary endpoints are:

- Proportion of patients with EASI-75 ( $\geq 75\%$  improvement from baseline) at week 16 (this is not a secondary endpoint for ex-US countries as it is already a co-primary endpoint)
- Percent change in EASI score from baseline to week 16
- Percent change from baseline to week 16 in weekly average of daily peak Pruritus NRS
- Proportion of patients with improvement (reduction) of weekly average of daily peak Pruritus NRS  $\geq 3$  from baseline at week 16
- Proportion of patients with improvement (reduction) of weekly average of daily peak Pruritus NRS  $\geq 4$  from baseline at week 16

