##### Peak Pruritus Numeric Rating Scale (NRS)

The Peak Pruritus NRS is a simple assessment tool that patients will use to report the intensity of their pruritus (itch) during a 24-hour recall period. Patients will be asked the following questions:

- For maximum itch intensity: “On a scale of 0 to 10, with 0 being ‘no itch’ and 10 being the ‘worst itch imaginable’, how would you rate your itch at the worst moment during the previous 24 hours?”

Patients will be instructed on using the patient diary to record their Pruritus NRS score at the baseline visit. Patients will complete the rating scale daily throughout the entire study (screening period, treatment period, and follow-up period). Clinical sites will check and remind patients to complete the diary at each visit.

For each day, if there are multiple NRS scores collected on the same day, the maximum value of all the scores collected will be used for analysis.

The baseline NRS is defined as the prorated average of the NRSs reported continuously for 7 days right before and on the baseline visit (i.e. study day -6 to day 1). For post-baseline NRS, the mean weekly NRS is calculated as the prorated average of the reported daily NRS within the week. For example, if there are 3 scores in a week, the prorated average =  $(\text{score1} + \text{score2} + \text{score3})/3$ .

Other secondary endpoints are:

- Proportion of patients with EASI-50 at week 16
- Proportion of patients with EASI-90 at week 16
- Time to onset of effect on pruritus as measured by proportion of patients with improvement (reduction) of weekly average of daily peak Pruritus NRS  $\geq 3$  from baseline during the 16-week treatment period

- Time to onset of effect on pruritus as measured by proportion of patients with improvement (reduction) of weekly average of daily peak Pruritus NRS  $\geq 4$  from baseline during the 16-week treatment period
- Change from baseline to week 16 in percent BSA affected by AD
- Percent change from baseline to week 16 in SCORAD
- Change from baseline to week 16 in CDLQI
- Change from baseline to week 16 in POEM
- Change from baseline to week 16 in weekly average of daily peak Pruritus NRS
- Percent change from baseline to week 4 in weekly average of daily peak Pruritus NRS
- Change from baseline to week 16 in HADS
- Proportion of patients with improvement (reduction) of weekly average of daily peak Pruritus NRS  $\geq 4$  from baseline to week 4

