#### **5.7.2. Analyses of Secondary Efficacy Variables**

The binary secondary efficacy endpoints will be analyzed using the same approaches as that are used for the analysis of the primary endpoints.

The endpoint "Proportion of patients with improvement (reduction) of weekly average of daily peak pruritus NRS  $\geq 4$  from baseline to week 16" will only be analyzed for patients with baseline peak pruritus NRS  $\geq 4$ . Similarly the endpoint "Proportion of patients with improvement (reduction) of weekly average of daily peak pruritus NRS  $\geq 3$  from baseline to week 16" will only be analyzed for patients with baseline peak pruritus NRS  $\geq 3$ .

The continuous endpoints will be analyzed using the multiple imputation (MI) with analysis of covariance (ANCOVA) model as the primary analysis method. Patients' efficacy data through week 16 after the rescue treatment use will be set to missing first, and then be imputed by the multiple imputation method. Missing data from the FAS will be imputed 40 times to generate 40 complete data sets by using the SAS procedure MI following the 2 steps below:

- Step 1: The monotone missing pattern is induced by Markov Chain Monte Carlo (MCMC) method in MI procedure. The monotone missing pattern means that if a patient has missing value for a variable at a visit, then the values at all subsequent visits for the same variable are all missing for the patient.
- Step 2: The missing data at subsequent visits will be imputed using the regression method for the monotone pattern with adjustment for covariates including treatment groups, randomization strata (disease severity, age group), and relevant baseline.

The week 16 data of each of the 40 complete datasets will be analyzed using an analysis of covariance (ANCOVA) model with treatment, randomization strata (disease severity, age group), and relevant baseline included in the model, and the SAS MIANALYZE procedure will be used to generate valid statistical inferences by combining results from the 40 analyses using Rubin's formula.

The imputation model will include:

- The covariates included in the ANCOVA model, including the treatment group, the baseline value and the randomization strata (disease severity, weight group)
- Measured endpoint values at every clinic visit (i.e. week 1, 2, 3, 4, 8, 12 and week 16)

Categorical variables included in above model (i.e., treatment group and randomization strata) are not expected to be missing.

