#### 6.4. Analysis Visit Window

Data analyzed by-visit-analysis (including efficacy, laboratory data, visit sign, and ECG) will be summarized by the study scheduled visits described in the study protocol and SAP, “Schedule of Event”. The analysis visit windows will be exhaustive so that all available values obtained from unscheduled visits, early termination (ET) visit and end of treatment (EOT)/end of study (EOS) have the potential to be summarized. No analysis visit windows will be applied for the study scheduled visits.

The following analysis visit windows will be used to map the unscheduled visits, ET and EOT/EOS visits, based on the study day:

Visit	Target Day	Analysis Time Window Based on Study day*
Screening	<1	<1
Baseline	1	1
Week 1	8	[2,11]
Week 2	15	[12,18]
Week 3	22	[19,25]
Week 4	29	[26, 43]
Week 8	57	[44, 71]
Week 12	85	[72, 99]
Week 16	113	[100, 127]
Week 20	141	[128, 155]
Week 24	169	[156, 183]
Week 28	197	>=184

\*study day is calculated relative to the date of first study drug injection.

In general, the following order will be used to select the record for analysis at given visit:

1. Scheduled visit
2. Early termination (ET) or end of study (EOS), whichever comes first if scheduled visit not available
3. Unscheduled visit if both scheduled visit and ET/EOT/EOS are not available

For the multiple measurements of the same test in the same window, the following rules will be used to pick up the analysis value:

- If multiple valid values of a variable within an analysis visit window, the closest from the target study day will be selected.
- If the difference is a tie, the value after the targeted study day will be used.

- If multiple available values of a variable exist within a same day, then the first value of the day will be selected.

Both scheduled and unscheduled measurements will be considered for determining abnormal/PCSV values from laboratory, vital sign or ECG as well as the baseline values.

For the daily collected ePRO except TNSS data, the analysis visit windows will be implemented following the procedure below:

Step 1: Derive the study day

- If diary date  $\geq$  1st injection date, then diary study day = diary date – 1st injection date +1
- Otherwise diary study day = diary date – 1st injection date

Step 2:

- Windows are defined as -6 to 1 = BL, 2 to 8 = week 1, 9 to 15 = week 2, etc., with 7 days interval between visit windows.

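### The imputation model for weekly pruritus NRS lists only the seven clinic weeks, so nine available weekly diary means are not used to impute week 16

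*SAP*

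**What the plan says.** SAP section 5.7.2 sets the primary method for every continuous endpoint: "The continuous endpoints will be analyzed using the multiple imputation (MI) with analysis of covariance (ANCOVA) model as the primary analysis method". Data after rescue are set to missing and imputed 40 times. The section then lists what the imputation model contains: the ANCOVA covariates and "Measured endpoint values at every clinic visit (i.e. week 1, 2, 3, 4, 8, 12 and week 16". No separate model is given for NRS. Protocol section 9.5.2.2 describes the same two imputation steps without a visit list.

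The list matches the visits at which EASI, SCORAD and BSA are scored. NRS is collected differently. SAP section 4.4.2 says "Patients will complete the rating scale daily throughout the entire study" and that "the mean weekly NRS is calculated as the prorated average of the reported daily NRS within the week". SAP section 6.4 assigns diary days to consecutive windows: "2 to 8 = week 1, 9 to 15 = week 2, etc., with 7 days interval between visit windows". After week 4 the clinic schedule thins to "in-clinic visits every 4 weeks through week 16 with weekly telephone visits in between" (SAP section 2.3), but the diary continues.

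The main endpoint affected is a key secondary one: "Percent change from baseline to week 16 in weekly average of daily peak Pruritus NRS". It is tested at positions 4 (Q2W) and 12 (Q4W). Absolute change in weekly NRS at week 16 is at positions 23 and 31.

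**The concern.** Imputing week 16 after rescue or dropout relies on the data being missing at random given what is in the model. Protocol section 5.3 allows rescue for intolerable symptoms at the investigator's discretion, with an unscheduled visit if needed, so it is plausible that rescue often follows a recent rise in itch. SAP Appendix 10.5 classes topical corticosteroids, tacrolimus and crisaborole automatically as rescue only after day 29, which is when clinic visits become four-weekly. For such patients the weekly means just before rescue are the values most likely to explain why later data are missing. They are available, and the listed model does not use them.

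If that mechanism operates, imputed week-16 values come out somewhat too favourable, more so in the arm with more rescue, and the difference from placebo shrinks. Testing is strictly sequential, so precision lost at position 4 bears on every later position.

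**Working it through.** **1. Nearest stated figure.** The documents give no SD, power or missing-data rate for continuous NRS. The closest figure is power for an NRS reduction of at least 4 points, n = 80 per group, two-sided 0.05 (SAP section 2.2). The formula is power = Φ[(d − 1.96·SE0)/SE1], with pooled SE0, unpooled SE1, and d = p1 − p2, less 1/80 if continuity-corrected.

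- Q2W, 38% vs 11%: SE0 = √(2×0.245×0.755/80) = 0.0680; SE1 = √((0.2356+0.0979)/80) = 0.0646. Power is 98.3%, or 97.3% corrected; the plan states 97%.
- Q4W, 36% vs 11%: 96.8%, or 95.1% corrected; the plan states 95%.

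Both reproduce with the correction. This endpoint is binary and uses non-responder imputation, so the present point does not change it.

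**2. Weeks left out.** Diary week w covers days 7(w−1)+2 to 7w+1, so week 5 is days 30-36, week 15 is days 100-106 and week 16 is days 107-113. The weeks not listed are 5, 6, 7, 9, 10, 11, 13, 14 and 15: 9/15 = 60% of the post-baseline weekly means before week 16. A patient last observed at week 7, 11 or 15 is imputed from week 4, 8 or 12, losing the three latest means. A patient last observed at weeks 1-4, 8 or 12 loses no recent week.

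**3. Information lost per patient (assumed correlations, total SD 2.2).** Residual variance of week 16 is S16,16 − S16,o·Soo⁻¹·So,16, where o is the set of observed weeks used. The pure AR(1) case with weekly correlation 0.9 can be checked by hand. Last observed at week 15:

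- Clinic list (lag 4 from week 12): R² = 0.9⁸ = 0.43, residual SD = 2.2×√0.57 = 1.66.
- All weeks (lag 1): R² = 0.9² = 0.81, residual SD = 2.2×√0.19 = 0.96.

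Across four correlation structures:

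| Last observed week | Residual SD, clinic weeks | Residual SD, all weeks |
|---|---|---|
| 15 | 1.51-1.89 | 0.95-1.33 |
| 11 | 1.71-2.01 | 1.58-1.93 |
| 7 | 1.81-2.11 | 1.74-2.03 |

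**4. Effect on the difference if rescue follows the latest weekly NRS.** Every rate, SD and correlation here is an assumption.

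Large-sample monotone regression imputation, 150,000 per arm, SD 2.0, true difference about −2.0 NRS points, two correlation structures:

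| Missing at week 16, placebo / active | Clinic weeks | All weeks |
|---|---|---|
| about 30% / 21% | −2.00, −1.97 | −2.01, −1.99 |
| about 50% / 33% | −1.94, −1.93 | −1.99, −2.00 |
| 61-68% / 39-43% | −1.87, −1.81 | −2.00, −1.99 |

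The clinic-week model put the placebo mean 0.03-0.31 points too low and the active mean 0.02-0.12 too low, which is why the difference shrinks.

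On the percent-change scale:

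- 400 trials of 80 per arm, about 50% / 29% rescued: full data −27.1, clinic weeks −26.3, all weeks −27.1. RMSE against full data fell from 2.8 to 2.6. Shrinkage is 0.8/27.1 = 3%.
- A second set at 80 per arm, 29% / 11% and 45% / 21% rescued: shrinkage about 1.0-1.5 points, nearly all removed by using all weeks. RMSE fell from 2.0 to 1.6 and from 2.8 to 2.2.
- 60,000 per arm, full-data difference −27.6 to −28.1: shrinkage 0.5, 0.9 and 1.3 points at 21% / 9%, 38% / 18% and 54% / 30% rescued.

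**5. Other mechanisms.**

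- Rescue follows NRS at the last clinic visit: shrinkage within 0.1 points up to 55% / 32% rescued. At 80 per arm both models were unbiased with about equal RMSE.
- Rescue follows a correlated skin score: 0.1-0.3 points at 10-42% placebo rescue.
- No treatment effect: bias within 0.4 points, similar for both models.

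**The case against.** **The exclusion is inferred.** The SAP nowhere says that weekly NRS means are discarded. The list looks like general text written for investigator-scored endpoints. That is probably its origin, but it is introduced as exhaustive, it governs all continuous endpoints, and nothing else brings the other weeks in. Read the other way, the NRS model would be unspecified and a sentence would still be needed.

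**The bias depends on the mechanism.** This stands. A reader might infer that the clinic-week list makes imputed values too favourable as a matter of course. The documents do not support that: they give no rescue rates and no rule linking rescue to recent itch, and under rescue driven by the last clinic value the bias disappears.

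**The late-rescue case carries little of the effect.** A reader might take rescue in week 15, with weeks 13 and 14 ignored, as the main driver. In the 400-trial simulation, adding only weeks 13-15 moved the estimate from −26.3 to −26.5, which is 0.2 of the 0.8-point gap. The omitted weeks matter together.

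**Other analyses give partial cover.** SAP section 5.7.2 plans LOCF, WOCF and an all-observed-data MI analysis for EASI and/or NRS. In the last, a rescued patient with week-16 diary data needs no imputation. But it answers a different question about rescue, and none of the three changes the primary imputation model.

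**A longer model has a price.** Sixteen correlated weekly means, with no minimum number of post-baseline diary days, can bring more intermittent gaps and noisier means into the MCMC step. The simulations used only the monotone regression step (with 10 imputations in the 400-trial set), so this cost was not tested. It justifies a convergence check and a fallback.

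**Conclusion.** The point holds as a modest, inexpensive improvement. As written, the model for the week-16 continuous NRS endpoints leaves out nine weekly means that the plan itself derives. If rescue or dropout follows recent worsening between visits, the clinic-week model shrinks the difference by about 0.5 to 1.5 percentage points on about 27 (roughly 2% to 6%), less with less rescue. If rescue follows the last clinic-visit value, there is essentially no bias. These sizes rest wholly on assumed variances, correlations and rescue rates.

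A reader might also infer a threat to the validity of a positive result. That is not supported: the bias runs toward the null, and no type I error inflation has been shown (rejection rates under the null were not simulated). The binary NRS endpoints use non-responder imputation and are unaffected, as are the stated powers. The week-4 NRS percent change is little affected because weeks 1-4 are all in the model.

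**What to change.** In SAP section 5.7.2, state that for percent change and change in weekly average peak Pruritus NRS at week 16 the imputation model includes all weekly means from week 1 to week 16. Keep the clinic-visit list for clinic-assessed scores. State also which weeks the LOCF and WOCF analyses of NRS use.

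The cost is one or two sentences and a longer variable list (16 time points rather than 7). Because intermittent gaps may increase, require a check of MCMC convergence and name a reduced set of weekly means in advance as the fallback. Settle this before database lock and unblinding.

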#### Sensitivity analyses

In addition to the MI method described previously, sensitivity analyses for the continuous endpoints for EASI and/or Pruritus NRS will be conducted as described below.

1. The sensitivity analysis based on all observed data regardless if rescue treatment is used or data is collected after withdrawal from study treatment using MI method will be performed.
2. This sensitivity analysis will use ANCOVA model, including the treatment group, the baseline value and the randomization strata. The efficacy data will be set to missing after rescue treatment is used. The post-baseline LOCF method will then be used to impute missing values.
3. This sensitivity analysis will use ANCOVA model, including the treatment group, the baseline value and the randomization strata. The efficacy data will be set to missing after rescue treatment is used. The post-baseline worst observation carried forward (WOCF) method will then be used to impute missing values.

Time to onset of effect on pruritus as measured by proportion of patients with improvement (reduction) of weekly average of daily peak Pruritus NRS  $\geq 4$  from baseline during the 16-week treatment period will be calculated for each patient as (the date of having the first event - the first study drug dose date + 1 day. Patients not having any event during the treatment period will have their time censored at the end of treatment period. Time to onset of effect on pruritus will be analyzed using the Cox proportional hazards model including treatment and randomization strata as factors. The hazards ratio, its 95% confidence interval and p-value will be reported. Kaplan-Meier curves will be provided.

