## 2. INVESTIGATIONAL PLAN

### 2.1. Study Design and Randomization

[figure not shown]
This is a randomized, double-blind, placebo-controlled, parallel-group study to investigate the efficacy and safety of dupilumab monotherapy in pediatric patients with moderate-to-severe AD. The study population will include patients  $\geq 12$  years to  $< 18$  years of age with moderate-to-severe AD whose disease cannot be adequately controlled with topical medications or for whom topical treatment is medically inadvisable (eg, intolerance, other important side effects or safety risks).

Patients who continue to meet eligibility criteria at baseline will undergo day 1/baseline assessments and will be randomized in a 1:1:1 ratio stratified by baseline weight group ( $< 60$  kg and  $\geq 60$  kg; each weight stratum will enroll approximately 120 patients) and baseline disease severity (moderate [IGA=3] vs. severe [IGA=4] AD) as follows:

- Dupilumab Q2W treatment group: Patients with baseline weight  $< 60$  kg will receive Q2W subcutaneous (SC) injections of 200 mg dupilumab following a loading dose of 400 mg on day 1. Patients with baseline weight  $\geq 60$  kg will receive Q2W SC injections of 300 mg dupilumab following a loading dose of 600 mg on day 1.
- Dupilumab Q4W treatment group: Patients will receive Q4W SC injections of 300 mg dupilumab following a loading dose of 600 mg on day 1, irrespective of weight.
- Placebo treatment group: Patients will receive placebo matching dupilumab Q2W (including doubling the amount of placebo on day 1 to match the loading dose). In order to maintain blinding for the study, patients in the  $< 60$  kg weight stratum will receive, in a 1:1 ratio, either placebo matching 200 mg dupilumab (including doubling the amount of placebo on day 1 to match the loading dose) or placebo matching 300 mg dupilumab (including doubling the amount of placebo on day 1 to match the loading dose). In the  $\geq 60$  kg weight stratum, the patients randomized to the placebo group will receive placebo matching 300 mg dupilumab (including doubling the amount of placebo on day 1 to match the loading dose).

In order to maintain blinding, all patients will receive an injection Q2W from day 1 to week 14. Patients will receive placebo injection at the weeks dupilumab is not given.

Below diagram shows the planned number of patients in each dose group.

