## 2.2. Sample Size and Power Considerations

Approximately 240 patients are planned to be randomized to 1 of the following treatment groups:

- Dupilumab Q2W treatment group: 200 mg Q2W patients <60 kg or 300 mg Q2W patients ≥60 kg
- Dupilumab Q4W treatment group: 300 mg Q4W
- Placebo group

It is estimated that with 80 patients per group, at the 2-sided 5% significance level, the study will have:

- 98% power to detect a difference of 28% between dupilumab Q2W treatment and placebo treatment in the percentage of patients who achieve an IGA score 0 to 1 at week 16, assuming that the percentages are 37% and 9% for dupilumab Q2W and placebo, respectively.
- 88% power to detect a difference of 20% between dupilumab Q4W treatment and placebo treatment in the percentage of patients who achieve an IGA score 0 to 1 at week 16, assuming that the percentages are 29% and 9% for dupilumab Q4W and placebo, respectively.
- 99% power to detect a difference of 35% between dupilumab Q2W treatment and placebo treatment in the percentages of patients achieving EASI-75 response at week 16, assuming that the percentages are 48% and 13% for dupilumab Q2W and placebo, respectively.
- 99% power to detect a difference of 32% between dupilumab Q4W treatment and placebo treatment in percentages of patients achieving EASI-75 response at week 16, assuming that the percentages are 45% and 13% for dupilumab Q4W and placebo, respectively.

[figure not shown]
Additional power calculation based on the key secondary endpoint “proportion of patients with improvement (reduction) of Pruritus NRS  $\geq 4$  from baseline to week 16”, with 80 patients per group, the study will provide:

- 97% power at a 0.05 level to detect a difference of 27% in the percentages of patients achieving Pruritus NRS reduction  $\geq 4$  at week 16, assuming that the percentages are 38% and 11% for dupilumab Q2W and placebo, respectively.
- 95% power at a 0.05 level to detect a difference of 25% in the percentages of patients achieving weekly average of daily peak Pruritus NRS reduction  $\geq 4$  at week 16, assuming that the percentages are 36% and 11% for dupilumab Q4W and placebo, respectively.

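### The Cox model for time to onset of pruritus effect omits baseline Pruritus NRS; the tests stay valid, but the hazard ratio is pulled toward 1 and a little power can be lost

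*SAP*

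**What the plan says.** The time-to-onset analysis stands in SAP 5.7.2, at the end of the text under Sensitivity analyses: "Time to onset of effect on pruritus will be analyzed using the Cox proportional hazards model including treatment and randomization strata as factors". On censoring: "Patients not having any event during the treatment period will have their time censored at the end of treatment period". The derivation is written out only for the 4-point threshold; the 3-point version gets the same model by implication.

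The strata are disease severity (IGA 3 or 4) and weight group, as in SAP 2.1: patients "will be randomized in a 1:1:1 ratio stratified by baseline weight group" and by baseline severity. Neither measures itch.

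For the continuous endpoints, including NRS change, the same SAP section does adjust for baseline. The imputation model contains "The covariates included in the ANCOVA model, including the treatment group, the baseline value and the randomization strata (disease severity, weight group"), and the ANCOVA includes the relevant baseline. The binary NRS responder endpoints use CMH on the strata alone.

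The multiplicity table in SAP 5.7.2 puts the 3-point version at ranks 17 (Q2W) and 25 (Q4W) and the 4-point version at 18 and 26. Each rank is tested only if the one before it is significant.

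**The concern.** The event is defined relative to baseline. Protocol 4.2.1, criterion 6, requires a baseline average of at least 4 on a 0 to 10 scale. A patient who enters at 4 must average 0 for a week to show a 4-point fall; one who enters at 9 need only reach 5. Regression to the mean works in the same direction. So baseline NRS is a plausible predictor of onset, and the strata do not stand in for it.

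In a Cox model, leaving out a prognostic covariate does not widen the standard error of the treatment effect. It moves the estimated log hazard ratio toward 0, so the Wald statistic shrinks when there is a true effect. At stake is some power at four ranks. Ranks 19 to 40 can be tested only if 17 and 18 succeed.

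**Working it through.** **Inputs from the documents.** On sample size and alpha: "It is estimated that with 80 patients per group, at the 2-sided 5% significance level, the study will have" the powers listed in SAP 2.2. For a 4-point reduction at week 16, the assumptions are 38% (Q2W) and 36% (Q4W) against 11%. No hazard ratio or power is given for time to onset.

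**Assumed inputs.** Baseline NRS normal with mean 7.5 and SD 1.5, clipped to 4–10; hazard ratio per baseline point from 1.0 to 2.0; weekly event times over 16 weeks; Efron ties; two-sided Wald test at 1.96.

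**1. The plan's nearest figure.** SAP 2.2 claims "97% power at a 0.05 level to detect a difference of 27% in the percentages of patients achieving Pruritus NRS reduction" of at least 4, "assuming that the percentages are 38% and 11% for dupilumab Q2W and placebo, respectively". With pooled rate p̄ = 0.245:
- SE under H0 = √(2 × 0.245 × 0.755 / 80) = 0.0680
- SE under H1 = √((0.38 × 0.62 + 0.11 × 0.89) / 80) = 0.0646
- Power = Φ((0.27 − 1.96 × 0.0680) / 0.0646) = 98.3%
- With a continuity correction of 1/80 subtracted from the difference: 97.3%

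For Q4W the same steps give 96.8% and 95.1%, against a stated 95%. The plan's figures reproduce.

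**2. Proportional-hazards simulation** (80 v 80, 600 trials per row, true conditional log HR 0.85). Each cell gives mean log HR / SE, then power.

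| HR per baseline point | Strata only | Strata + baseline NRS | Power difference (points) |
|---|---|---|---|
| 1.0 | 0.878 / 0.329, 78.7% | 0.882 / 0.331, 78.5% | −0.2 |
| 1.2 | 0.873 / 0.327, 78.5% | 0.889 / 0.329, 79.8% | 1.3 |
| 1.4 | 0.843 / 0.320, 77.2% | 0.884 / 0.322, 80.3% | 3.1 |
| 1.7 | 0.785 / 0.306, 73.5% | 0.876 / 0.310, 81.3% | 7.8 |
| 2.0 | 0.734 / 0.294, 73.0% | 0.884 / 0.300, 84.8% | 11.8 |

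The SE rises slightly with adjustment in every row. The gain comes from the numerator: in the last row the mean log HR over SE goes from 0.734/0.294 = 2.50 to 0.884/0.300 = 2.95.

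At log HR 1.30, close to the plan's effect, power is 98.7% or more without baseline and 99.8% or more with it. The largest difference is 1.1 points (98.7% to 99.8%, at 2.0 per point).

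**3. NRS trajectories calibrated to week-16 response** (300 trials each).
- Percent fall independent of baseline (baseline HR about 1.29 per point for the 4-point threshold): at 38% v 11%, SE 0.312 to 0.314, log HR 1.350 to 1.392, power 100% either way. At 36% v 11%, power 99.3% to 99.7%. At a weaker 23% v 11%, power 66.3% to 70.0% (4-point) and 78.3% to 79.0% (3-point).
- Absolute fall independent of baseline: 66.7% to 67.3% at 23% v 11%, so essentially no gain.
- Proportional fall with baseline noise of SD 0.8 (400 trials, baseline HR 1.4–1.5 per point): at a reduced effect, 63.5% to 72% (3-point) and 57% to 61% (4-point); near the plan's effect (33% v 10%), 97.5% to 99% (4-point).
- A further run near 38% v 11% gave 98.4% to 99.2% (4-point).

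**4. Type I error.** With no treatment effect, the strata-only test rejected in 3.3% to 5.5% of 600 trials and the adjusted test in 3.5% to 6.8%. Monte Carlo error is √(0.05 × 0.95 / 600) = 0.9 points. The strata-only test is valid. The 6.8% is the highest of five settings and about two Monte Carlo errors above 5%.

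**5. The gate.** Rank 17 is reached only after ranks 1 to 16, which include NRS response at both thresholds in both regimens (5, 6, 13, 14). At 23% v 11%, rank 6 alone has power Φ((0.12 − 1.96 × 0.0594) / 0.0586) = 52%. A weak effect would therefore often stop the sequence before any onset test. Restricted to trials that pass the NRS responder tests, simulated gains were about 0 to 4 points.

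**The case against.** The strongest case for leaving the model alone has four parts.

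- **It follows a convention.** Protocol 9.1 commits only to the two stratification factors, the closest analogues (the binary NRS responder tests) use strata-only CMH, and the safety Cox models in SAP 5.8.1 also use treatment and strata. This stands. The difference from the ANCOVA is a choice, not a contradiction.
- **The size is negligible at the design effect.** This stands too: 0 to 2 points.
- **The association is unquantified.** True. If absolute change does not depend on baseline, the gain is about nil.
- **Adjustment changes the estimand.** True: the hazard ratio becomes conditional on baseline NRS. Under the null both models test the same absence of effect.

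Three stronger readings are tempting but unsupported. A reader might infer lost precision from the linear-model argument; the SE is in fact equal or slightly smaller without baseline. A reader might infer that the p-values are invalid; the null runs show no such problem. A reader might infer that everything from rank 19 down is endangered; a trial that reaches rank 17 has already shown significant itch response at both thresholds in both regimens.

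The SAP also names no method for ties, although onset can take only about 16 weekly values. Assuming Breslow from a software default goes beyond the text. Where Breslow and Efron were compared, power differed by 3.5 points in one weak-effect setting and by 0 to 1.5 points in others.

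**Conclusion.** The omission is real and its consequence is small. The strata-only Cox test is valid and not less precise, but it estimates an attenuated hazard ratio if baseline NRS predicts onset. The power cost is about 0 to 2 points at 38% v 11%. At weaker effects it is about 0 to 8 points with a mild to moderate association, and about 12 only at a hazard ratio of 2.0 per baseline point. Gating by ranks 1 to 16 reduces it further.

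These sizes rest on the assumed baseline distribution, strength of association and shape of the itch trajectory, none of which the documents supply. Monte Carlo error on a single power near 70–80% is about 1.6 to 2.7 points; paired differences are tighter. The largest power loss from adjusting was 0.2 points, when baseline had no effect. The point is a cheap improvement of minor severity.

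**What to change.** Amend the time-to-onset sentence in SAP 5.7.2 so that, for both the 3-point and 4-point thresholds, the Cox model contains treatment, disease severity, weight group and the baseline weekly average of daily peak Pruritus NRS as a continuous covariate. Efron handling of ties can be named in the same sentence; this is optional. The amendment must precede any unblinding, including the first-step analysis in SAP 7 if it is performed, because that analysis is final for the secondary endpoints.

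The cost is one sentence and no new data: baseline NRS is an entry requirement with at least 4 of 7 daily scores. The reported hazard ratio becomes conditional on baseline NRS as well as the strata and should be labelled so. The strata-only model can be kept as a supportive analysis, and the planned Kaplan-Meier curves are unaffected.
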